[figure not shown]

Official Title: Effect of supplementation with *Euterpe edulis* on the physical and mental performance of healthy men submitted to physical exercises

Ethical committee Protocol No: 6.202.888

Study protocol

1. Type of study

This is a clinical study, double blind, with the purpose of offering the juice of *E. edulis*, daily for 4 weeks before the day of the final evaluation, compared to the control. There will be about 40 men, aged 19 to 30 years, who perform regular physical exercises, in total of 150 min per week, at a minimum of 3 months.

2. Experimental Protocol

The men will be randomized into two groups, called GJ who will receive the sample and GP who will receive the placebo. The sample consists of 250 mL of juçara juice and the placebo which is 250 mL of water with pectin and natural dye. Research subjects will maintain their exercise routine, as well as fill out a food diary that will be sent electronically. The research will be for 11 days, and on day 1 (D1) of the research he will have the blood collected. On day 11 of the D11 survey, at time zero he will have the blood collected, and then consume the sample or the placebo. Two hours after he will be subjected to the battery of exercises, following 1. Dorsal dynamometer, 2. shoulder dynamometer, 3. manual dynamometer, 4. ergospirometry + electrocardiogram + digital lactate, 5. jump test for 1 min (amounts of jumps), 6. Pollock abdominal test and 7. functional mobility test. At the end, the blood will be collected, and a psychological form will be applied. After 2 and 7 days of physical exercise will be applied visual pain test.

3. The size of the sample

The calculation of the sample of patients for this study was performed using the software G*Power3.1.9.7 (Public domain). Considering the alpha value equal to 0.05 and the power of test $1 - \beta$ as 95% (0.95, that is, determining that the probability of type II error (β) should not be greater than 5%), the value of 20 patients was reached.

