The selection will be simple random probabilistic from a total population of patients who fit the inclusion criteria. Among the inclusion criteria are: being male, aged between 19 and 30 years and practicing physical exercises regularly for at least 3 months. Among the exclusion criteria are people who have motor problems, cardiovascular changes, have type I and II diabetes, smokers, athletes, cognitive deficits, and psychomotor disorders. Each patient will be evaluated at the beginning of the exercise and at the end of the exercise. Patients were randomly divided into 2 groups: treatment with placebo product and with the supplement of *E. edulis*.

4. Ethical issues

The study will be conducted after approval by the Ethics Committee on Research with Human Beings of the Vila Velha University and conducted in accordance with the Declaration of Helsinki. The clinical study will also be registered with REBEC, and will only be initiated after all ethical approvals. All participants will sign a written agreement (ICF).

As for the risks, in a previous study with 39 participants, none presented pictures of allergy or gastric or intestinal intolerance to JFJ and as a benefit, such a study demonstrated a positive effect on the acute adaptive inflammatory response (MENDES et al., 2021).

5. Inclusion criteria

Among the inclusion criteria are:

- Being male
- Aged between 19 and 30 years old
- Practicing physical exercises regularly for at least 3 months

6. Exclusion Criteria

Men who use:

- Steroids
- Anabolics
- Taurine
- BCCA
- Exogenous supplementation

7. Removal criteria

Among the exclusion criteria are people who have:

- Motor problems
- Cardiovascular changes
- Have type i and ii diabetes
- Smokers
- Athletes
- Cognitive deficits
- Psychomotor disorders.

Each patient will be evaluated at the beginning of the exercise and at the end of the exercise. Patients will be randomly divided into 2 groups: treatment with a placebo product and with an E. edulis supplement.

8. Intervention

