10.3 Collection of blood samples and analysis of biomarkers

In the blood collection will be collected samples of 8 ml of the cubital vein of the forearm of the patients according to the method used in Mendes et al. (2021). The samples will be stored in tubes containing ethylenediamine tetraacetic acid (EDTA) 10 or without anticoagulants. The serum should be acquired by the centrifugation method (1000 x g for 10 minutes at 4°C) and stored at – 80°C in polypropylene microcentrifuge tubes until analysis.

Pro-inflammatory biomarkers will contain acute phase proteins such as the cytokines TNF-alpha, IL-6, IL-1 beta, monocyte chemoattractant protein 1, and adhesion molecules. Anti-inflammatory markers: cytokines such as IL-10 and adiponectin that acts on muscles as anti-inflammatory cytokines (FANG et al., 2023).

The serum levels of the biomarkers will be determined by cytometry (flow cytometer FACSverse, BD Biosciences), using a commercial kit Cytometric Bead Array Human Inflammation kit, according to the manufacturer's instructions. Data will be analyzed using FCAP arrayTM (MENDES et al., 2021; SCHULZ et al., 2016)

Blood samples will be collected 1 hour before the high-intensity strength exercise, in the condition of muscle rest. From that moment the participants, randomly divided into two groups, will be selected to drink the extract of juçara (*Euterpe edulis*) or the placebo. New blood samples will be collected after the completion of the muscular effort, specifically 3 minutes after the exercise performed, in addition to the 3rd sample after 24 hours of rest.

Will be evaluated in the blood samples collected: plasma biomarkers, which include lactate concentration (LA). In plasma, creatine kinase (CK), total antioxidant capacity (TAC) and concentrations of testosterone (T), cortisol © and growth hormone (GH) will be analyzed. In addition to serum concentrations of inflammatory biomarkers such as interleukins (IL-6, IL-8, IL10) and TNF-alpha.

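### No check for acute infection or fever at entry, D1 or D11, although the blood outcomes are inflammatory markers and CK: a loss of precision, not a bias

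*Combined protocol and SAP*

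**What the plan says.** The criteria appear in three places in the combined protocol and SAP.

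- Section 3 (The size of the sample): "Among the exclusion criteria are people who have motor problems, cardiovascular changes, have type I and II diabetes, smokers, athletes, cognitive deficits, and psychomotor disorders".
- Section 6 (Exclusion Criteria) lists products used, from steroids to "Exogenous supplementation".
- Section 7 (Removal criteria) repeats the conditions of Section 3. It has no rule for a man who falls ill during the 11 days.

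The visits are described in Sections 2 and 8. D1 is a blood draw. D11 is a blood draw, the drink, the exercise battery two hours later, a second blood draw and a psychological form. No health question comes before either visit's sampling.

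The blood outcomes in Section 10.3 include CK, cortisol and "serum concentrations of inflammatory biomarkers such as interleukins (IL-6, IL-8, IL10) and TNF-alpha". Section 11 reports mean and SEM and tests by one-way repeated-measures ANOVA with Tukey's post hoc test. It states no transformation, outlier rule or sensitivity analysis.

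On size, Section 1 says "There will be about 40 men, aged 19 to 30 years", and Section 2 says "The men will be randomized into two groups, called GJ who will receive the sample and GP who will receive the placebo".

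**The concern.** The plan sets out to detect an effect of juice on markers that it classes as pro- or anti-inflammatory, but it does not ask whether a man has an acute inflammatory illness on the day the marker is measured. A man who met every criterion at entry could have an infection on D11 and still be sampled, tested and averaged.

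With about 20 men per arm, one extreme value carries weight: a shift of k standard deviations in one man moves his arm mean by k/20. What is at stake is the trial's ability to see a real effect on the cytokines and CK. If nothing is recorded at the visit, an ill man's outlier also cannot later be told apart from a genuine response, and removing it after the fact would be open to challenge.

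**Working it through.** **The plan's own figure.** Section 3 gives alpha 0.05, power 95% and the result: "the value of 20 patients was reached". It gives no effect size, SD or test family, and does not say whether 20 is per group or in total, so the figure cannot be reproduced forward. Solved backwards with the noncentral t (two equal groups, two-sided), 20 per group corresponds to a standardised difference d of 1.17, and 20 in total (10 per group) to d = 1.71. The plan therefore offers no marker-specific effect or SD to use below.

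**Inputs from the documents.** Two arms; about 40 men, so 20 per arm if allocation is equal (the ratio is not stated); means analysed untransformed.

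**Inputs assumed.** Marker log-normal with CV 50%; true reduction 35%; probability of illness on the test day 5%, the same in both arms; illness multiplies the marker by m = 2, 3 or 5.

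**How many ill men?** With r infections per man-year and t days of raised markers each, p = r × t / 365.

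- r = 2, t = 5: p = 2.7%, and 40p = 1.1 men expected.
- r = 3, t = 10: p = 8.2%, and 40p = 3.3 men expected.
- The chance of at least one ill man is 1 − (1 − p)^40: 67% and 97% for these two cases, and 1 − 0.95^40 = 87% at p = 5%.

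**Variance, by hand.** Scale the marker so that its healthy mean is 1. Its second moment is then 1 + 0.5² = 1.25 and its variance 0.25. Let W be 1 with probability 0.95 and m with probability 0.05. The new variance is 1.25 × E(W²) − E(W)².

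| m | E(W) | E(W²) | Variance | SD ratio to healthy |
|---|---|---|---|---|
| 2 | 1.05 | 1.15 | 0.335 | √(0.335/0.25) = 1.16 |
| 3 | 1.10 | 1.40 | 0.540 | √(0.540/0.25) = 1.47 |
| 5 | 1.20 | 2.20 | 1.310 | √(1.310/0.25) = 2.29 |

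Both arms scale alike, so these are also the ratios for the standard error of the difference.

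**Power, by simulation** (20,000 trials, two-sample t-test, two-sided 0.05; simulation error under one percentage point):

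| 5% ill, multiplier | Raw scale | Log scale |
|---|---|---|
| none ill | 76% | 80% |
| ×2 | 69% | 76% |
| ×3 | 57% | 71% |
| ×5 | 37% | 62% |

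The clean log-scale figure can be checked directly: the log SD is √ln(1.25) = 0.472, the log effect is −ln(0.65) = 0.431, so d = 0.431/0.472 = 0.91, which gives 80% power with 20 per arm.

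**False positives.** With no true effect, the raw-scale rejection rate goes from 4.8% with nobody ill to 4.3% at ×3 and 3.4% at ×5. It falls.

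**Second model.** With normal data, d = 1.17, 20 per arm and 5% ill, power falls from 95% to 91%, 69% or 41% for shifts of 2, 5 or 10 SD. The direction is the same, and a small shift again costs little.

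**The case against.** Several points against this carry weight.

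- *The lists are not presented as complete, and the official title calls the men healthy.* True, but no written criterion applies this to the day of testing. The term motor problems may already cover a current injury, so injury is not part of the main point; vaccination has no figure behind it either.
- *The loss rests on assumed inputs.* This stands. No illness rate, multiplier, CV or effect is in the documents, and that infection raises these markers on the day is itself an assumption. At ×2 the loss is only 7 percentage points. At 1% ill and ×3, power is still 71%.
- *The modelled test is not the planned one.* This stands too. Section 11 plans repeated-measures ANOVA. A man ill on D11 may be raised both before and after exercise, so a within-day change could be less affected. This was not modelled. The D1 sample might help with illness already present then, but no baseline adjustment is stated, and it cannot correct illness that starts later.
- *Much of the harm comes from untransformed means.* Partly so: the log scale recovers a good share of the loss, which is why it belongs in the fix.

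A reader might infer more than the plan supports. One inference is that a single cold in the placebo arm could produce a false claim of benefit; but illness is independent of blinded, randomised allocation, and the false-positive rate falls. Another is that ill men would reverse the direction of effect; in the model a wrong-signed difference occurs in about 2% of trials at ×3 and 7% at ×5, against 0.4% with nobody ill, and a significant one practically never. A third is that strength and ergospirometry results would be distorted as well; no calculation supports that here.

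**Conclusion.** The omission is real. Neither the exclusion and removal lists nor the D1 and D11 descriptions contain a check for acute infection or fever, while the blood outcomes are inflammatory cytokines and CK analysed as raw means. Followed as written, the plan averages acutely ill men in.

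The consequence is extra variance and lower power for the blood outcomes. Under the stated assumptions the raw-scale loss runs from modest (7 points at ×2) to large (39 points at ×5); if illness is rarer or milder, it is small. It is not a systematic bias, not a source of extra false positives, and not a demonstrated problem for the performance outcomes. The change is worth making because it is cheap and the information cannot be recovered later.

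**What to change.** 1. Add recent acute infection or fever, within a window set by the investigators, as a reason to defer enrolment before D1. Recent vaccination, or muscle injury not already covered by motor problems, can be added if the investigators wish.
2. Ask the same question on D11 before the drink, blinded to group, and record the answer.
3. Keep flagged men in the main analysis, so that the randomised comparison stays intact, and analyse the cytokines and CK on the log scale to limit the influence of extreme values.
4. Pre-specify a sensitivity analysis of the blood outcomes without the flagged men.

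Steps 2 and 4 do not restore the main analysis, because flagged men stay in it. The log scale protects that analysis in part (71% rather than 57% at ×3). The sensitivity analysis without flagged men has about 73% power on the raw scale, close to the 76% with nobody ill.

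The cost is one question at two existing visits, a few deferred enrolments and one extra analysis.

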On day 11 of the D11 survey, at time zero he will have the blood collected, and then consume the sample or the placebo. Two hours after he will be subjected to the battery of exercises, following 1. Dorsal dynamometer, 2. shoulder dynamometer, 3. manual dynamometer, 4. ergospirometry + electrocardiogram + digital lactate, 5. jump test for 1 min (amounts of jumps), 6. Pollock abdominal test and 7. functional mobility test. At the end, the blood will be collected, and a psychological form will be applied. After 2 and 7 days of physical exercise will be applied visual pain test.

9. Preparation of Juçara juice

The preparation will be obtained with the same methods already well established in previous studies (SCHULZ et al., 2016.; MENDES et al., 2021). Participants will receive 250 ml of water + purple dye + pectin (control) or commercial samples of juçara (*E.edulis*) refrigerated to 4°C to 10°C, per day, for 10 days, and on the 11th will be the exercise and on this day will be administered the juice of the juçara 2 h before on the day of the monitored exercise. The chemical characterization of *Euterpe edulis* will be with at least 350.0 + or - 17.5 mg of total phenolics (gallic acid equivalent), 186.0 + or - 7.5 mg of total monomeric anthocyanins (cyanidin 3-glycoside), 0.73 + or less 0.01 g of proteins, and 2.75 + or - 0.03 g of lipids (ether extract). During the 10 days of previous treatment, maintain the routine of physical exercises.

10. Values evaluated

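### The D11 performance battery estimates the daily course plus a same-day serving, and the one blood draw that bears on the daily course alone gets no between-arm comparison

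*Combined protocol and SAP*

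**What the plan says.** - **Purpose (section 1).** The study is described as one "with the purpose of offering the juice of" *E. edulis* every day for 4 weeks ahead of the final evaluation. Section 9 gives 10 days of daily intake with exercise on the 11th.
- **Design (sections 1 and 2).** "There will be about 40 men, aged 19 to 30 years"; "The men will be randomized into two groups, called GJ who will receive the sample and GP who will receive the placebo". The allocation ratio is not stated.
- **Test-day serving (section 9).** On the exercise day, "on this day will be administered the juice of the juçara 2 h before".
- **Blood and battery (sections 2 and 8).** On D11, "at time zero he will have the blood collected, and then consume the sample or the placebo". The seven-test battery starts two hours later, and blood is drawn again at the end. Section 2 also has a D1 blood draw. It does not say whether this precedes the first serving, and it schedules no performance test on D1.
- **A second blood schedule (section 10.3).** A resting sample 1 hour before exercise, then the drink, then samples 3 minutes after exercise and after 24 hours of rest. Neither the D1 sample nor the 10-day course is mentioned there.
- **Other tests.** The reaction-time tests (10.1, 10.2), the 6-minute step test (10.4.3) and the plank test (10.4.4) have no stated day or time.
- **Analysis (section 11).** One-way repeated-measures ANOVA with Tukey comparisons at p < 0.05. No arm factor, arm-by-time term, time point or contrast is named.

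**The concern.** The stated purpose points to a daily course, yet the battery is only ever done 2 hours after a further serving. No arm receives only the daily course or only the single drink, and no battery is scheduled without the D11 serving. If juice beats placebo on the battery, the result is likely to be reported as an effect of daily supplementation, although the serving taken that day could account for some or all of it.

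For biomarkers the schedule in sections 2 and 8 offers a way round this. The D11 time-zero blood follows the daily course and precedes that day's serving, and a D1 value is available for adjustment. Comparing the arms at that draw is the one randomised comparison that bears on the daily course alone. Section 11 does not specify it, so the draw would be collected without being used for the question it is best placed to answer.

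**Working it through.** **1. The plan's own figure.** Section 3 gives the inputs ("Considering the alpha value equal to 0.05 and the power of test" 95%, "determining that the probability of type II error (β) should not be greater than 5"%) and the answer, "the value of 20 patients was reached". It gives no effect size, SD, test or outcome, so 20 cannot be reproduced. Solving backwards for the standardised difference d, with a two-sided two-sample t-test at 95% power:

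- 20 in total (10 per arm): d = 1.71
- 20 per arm (40 in total, matching section 1): d = 1.17

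**2. What each measurement identifies.** Let C be the effect of the prior daily servings, A the effect of the D11 serving, and E any effect of the course on the response to exercise. The juice-placebo differences are:

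- Battery, D11: C + A. This is one equation for two unknowns (rank 1 of 2), so sample size cannot help.
- Blood, D1: 0, if drawn before the first serving.
- Blood, D11 time zero: C.
- Blood, post-exercise: C + A if effects are additive (rank 2 of 2), or C + A + E if not (rank 2 of 3).

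The between-arm difference in change from time zero to post-exercise is therefore A + E. It equals the single-drink effect only if E = 0, which the design cannot show.

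**3. What section 11 would deliver.** If the repeated factor is time, Tukey makes 3 pairwise comparisons over three draws (D1, time zero, post-exercise), or 6 over four if the 24-hour sample is added. D1 versus D11 time zero is among them, but it compares times, not arms.

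**4. Size of the missing comparison.** Assumptions: 1:1 allocation, two-sided alpha 0.05, two-sample t-test. Adjusting for D1 multiplies the detectable difference by √(1 − r²), where r is the D1–D11 correlation. The documents give no r, so 0.5 and 0.7 are assumed:

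- √(1 − 0.25) = 0.866
- √(1 − 0.49) = 0.714

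| Per arm | Power | Unadjusted (SD) | r = 0.5 | r = 0.7 |
|---|---|---|---|---|
| 20 | 80% | 0.909 | 0.909 × 0.866 = 0.787 | 0.909 × 0.714 = 0.649 |
| 20 | 95% | 1.170 | 1.170 × 0.866 = 1.013 | 1.170 × 0.714 = 0.835 |
| 10 | 80% | 1.325 | 1.325 × 0.866 = 1.147 | 1.325 × 0.714 = 0.946 |
| 10 | 95% | 1.706 | 1.706 × 0.866 = 1.477 | 1.706 × 0.714 = 1.218 |

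**5. Multiplicity.** Section 10.3 names at least 13 individual markers. One extra contrast each at 0.05 gives 13 × 0.05 = 0.65 expected false positives if nothing is affected.

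**The case against.** The best defence is that the regimen, including the test-day drink, is the intervention. The title speaks of supplementation in general, section 9 makes the D11 serving part of the schedule, and the documents nowhere promise to separate the daily course from a single drink. Juice versus placebo is then a sound randomised comparison. This stands: a reader might infer that the performance comparison is confounded or invalid, and it is not. Only the attribution is limited.

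Other parts of the defence also stand:

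- A reader might take it that every performance and mental outcome follows the serving. The documents show this only for the seven-test battery. For the reaction-time, step and plank tests the timing is missing.
- Section 11 does not say that it pools all times in one model. It is silent on both times and arms, and the lack of an arm term is the root defect. Once that is repaired, the time-zero comparison becomes available.
- Section 10.3 conflicts with sections 2, 8 and 9 on when blood is taken and when the drink is given. Until that is settled, the pre-serving sample is not uniquely defined.
- The time of the last serving before D11 is not stated, so the interval between it and the time-zero draw is unknown.

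What does not stand is that this is merely a preferred estimand. Section 1 frames the aim around daily intake before the evaluation, and the time-zero comparison answers that aim from draws already scheduled.

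**Conclusion.** The point holds in a limited form. The battery result is a valid estimate of the daily course plus a serving 2 hours before, and cannot be credited to the course alone. For biomarkers, the draw that bears on the course alone is in the schedule of sections 2 and 8, but section 11 plans no between-arm comparison there.

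With 20 per arm (an assumption, since section 3 does not say whether its 20 is per arm), that comparison detects 0.91 SD at 80% power and 1.17 SD at the plan's 95%. After adjustment for D1 the figures are 0.79 and 1.01 SD at r = 0.5, and 0.65 and 0.84 SD at r = 0.7. With 10 per arm they are larger, as tabulated. Only large effects would be found reliably. The attribution point itself does not depend on these numbers.

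Two stronger readings are not supported. The documents do not show that a single drink would explain a positive performance result; they leave the split unidentified. Nor does the change from time zero to post-exercise isolate the single drink, because the course may also alter the response to exercise. The matter is minor: it improves the analysis and the wording of conclusions and does not undermine the trial.

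**What to change.** First reconcile three things in the text, without which the contrast is not defined:

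- the blood and serving times in sections 2, 8 and 9 against those in section 10.3;
- the 4 weeks in section 1 against the 10 days in section 9;
- whether the D1 blood precedes the first serving. State also when the reaction-time, step and plank tests are done.

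Then, in section 11:

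1. Analyse each biomarker with arm, time and arm-by-time terms.
2. Pre-specify juice minus placebo at D11 time zero, adjusted for the D1 value, as the effect of the daily course. The adjustment is a true baseline adjustment only if D1 blood comes before the first serving.
3. Report the between-arm difference in change from time zero to post-exercise as a combined response (daily course, D11 serving and exercise), not as a single-drink effect.
4. Word conclusions from the battery as the effect of the daily course plus a serving 2 hours before.

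No added visit, sample or arm is needed. The costs are the reconciling text, one more contrast per biomarker (to be labelled secondary or corrected for multiplicity) and a narrower performance claim. Separating the two effects for performance would need a further test occasion or arm, which is not proposed here.

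### Men keep training up to the test day although the pre-exercise blood is meant to be a resting sample, and training is neither recorded nor limited beyond 24 hours after the test, which adds noise to CK, cytokines and strength and blurs the later pain scores

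*Combined protocol and SAP*

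**What the plan says.** **Training before the test.** Section 1 recruits men "who perform regular physical exercises, in total of 150 min per week, at a minimum of 3 months". Section 2 states "Research subjects will maintain their exercise routine, as well as fill out a food diary that will be sent electronically". Section 9 applies the same instruction to the supplementation period: "During the 10 days of previous treatment, maintain the routine of physical exercises". Neither section asks for a pause before a visit.

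**Rest around the test.** Section 10.3 states: "Blood samples will be collected 1 hour before the high-intensity strength exercise, in the condition of muscle rest". It does not say how long a man must have been at rest. The same section adds a further blood draw, "in addition to the 3rd sample after 24 hours of rest". That is the only timed rest in the document.

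**Pain.** Sections 2 and 8 both state: "After 2 and 7 days of physical exercise will be applied visual pain test". No activity rule goes with it.

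**Recording and analysis.** The only diary described is for food. Section 11 plans a one-way repeated-measures ANOVA with Tukey's test and has no term for training.

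**The concern.** A man who trained hard on the evening of day 10 and a man whose last session was on day 7 both follow sections 2 and 9. They may still arrive at D11 with different resting CK and cytokines and different strength. Section 10.3 treats both as rested. The D1 blood is exposed in the same way, without even a nominal rest condition.

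Every participant is affected, because regular exercise is an entry requirement. These markers are also the ones most directly tied to muscular effort, which is what the trial uses them to measure.

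After the first 24 hours, one man may rest until day 7 and another may resume his full routine. Their pain scores would then mean different things, and nothing recorded would tell them apart.

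Three things are at stake: precision, chance imbalance between two small groups, and how clearly the pain scores can be linked to the monitored exercise.

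**Working it through.** **1. The plan's own figures.** The plan gives no figure for training effects. Its only related figure is the G*Power result in section 3: 20 patients at alpha 0.05 and 95% power. That cannot be reproduced, because no effect size, SD, endpoint or test is stated. If 20 is read as the number per group (about 40 men in total) and a two-sided t-test is assumed, the implied standardized difference is d = 1.17.

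**2. The passages side by side.**

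| Period | Instruction on training | Measured |
|---|---|---|
| D1 | Routine maintained | Blood only |
| Up to day 10 | Routine maintained | None |
| D11, before exercise | Muscle rest, undefined | Blood |
| D11, battery and after | None | Strength and other tests, then blood |
| First 24 hours after | Rest (section 10.3) | Third blood sample |
| 24 hours to day 7 | No restriction or log stated | Pain at days 2 and 7 |

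**3. Illustrative size for log-CK at one time point.** Every input in this step is an assumption, except about 40 men in two groups.

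- Three sessions a week, unrelated to the visit day: p = 3/7 = 0.43 trained the day before.
- A previous-day session multiplies CK by k = 1.5 to 2.
- SD of log-CK without this effect: 0.5 (range 0.4 to 0.6).

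Added variance = p(1 − p)(ln k)², with p(1 − p) = 0.245:

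- k = 1.5: 0.245 × 0.405² = 0.040
- k = 2: 0.245 × 0.693² = 0.118

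| SD of log-CK | Variance | Rise, k = 1.5 | Rise, k = 2 |
|---|---|---|---|
| 0.4 | 0.16 | 25% | 74% |
| 0.5 | 0.25 | 16% | 47% |
| 0.6 | 0.36 | 11% | 33% |

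**4. Chance imbalance.** With 20 per group (equal allocation assumed), the SD of the difference in the proportion who trained the day before is √(2 × 0.245/20) = 0.156, about 16 percentage points.

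**5. What this would do to power.** At SD 0.5 the training share of total variance is 0.161/1.161 = 14% or 0.471/1.471 = 32%. Multiplying d = 1.17 by √(1 − share) gives 1.09 or 0.97. Power with 20 per group then falls from 95% to about 92% or 84%. This assumes that 95% was achieved without training noise.

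**6. Change scores.** If the previous-day effect multiplies the D11 pre- and post-exercise samples equally, it cancels in the log change and adds no variance. It need not cancel between D1 and D11, which are 10 days apart, so the weekday moves on by three. For a fixed Monday, Wednesday and Friday trainer, the answer to whether he trained the day before differs between the two visits when D1 falls on Monday, Tuesday, Wednesday or Thursday, that is, on 4 of 7 possible start days.

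**The case against.** **Rest is not absent.** Section 10.3 sets a rest condition for the pre-exercise sample and implies 24 hours of rest afterwards. A reader might infer that nothing limits training around the test, and that is too strong. What remains is that the first condition is undefined and the second ends before either pain score.

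**No one is told to train after D11.** Section 9 ties the instruction to the 10 days before the test, and section 2 describes 11 days of research. A reader might infer that every compliant man has completed a full training week by day 7, so that his score reflects that week. The documents make this possible, not required. A man who rested all week would comply equally.

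**Randomization and blinding protect the comparison.** A reader might infer that the juice-placebo contrast is biased. It is not, in expectation: private training adds noise to both groups, and chance imbalance is part of the test's ordinary error. The day-7 contrast can stand as a comparison in men living normally. Systematic bias would arise only if the juice itself changed training behaviour, and nothing in the documents suggests that it does. This objection stands. It limits the harm to noise and interpretation.

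**D1 is blood only.** Strength is listed only for D11 and pain only after it, so no D1 strength or pre-exercise soreness value exists to be disturbed.

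**The figures are assumed.** They concern log-CK at a single time point, whereas section 11 plans repeated measures. If the assumed SD came from men who train freely, it already contains the training effect, and the inflation is counted twice. No comparable figure can be given for cytokines, strength or pain. This also stands, so the figures show a plausible scale and are not an estimate.

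Testing under habitual training is a defensible choice. It does not explain a resting sample with no definition of rest, or the absence of any training record.

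**Conclusion.** The point holds in a limited form. The instruction to keep training and the requirement for a resting sample are not reconciled, training is neither recorded nor adjusted for, and activity between 24 hours and day 7 is left open. The results are extra between-man noise and possible chance imbalance in D1 and D11 resting CK and cytokines and in D11 strength, and a weaker link between the monitored exercise and pain at day 2 and especially day 7.

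On the assumptions shown, the variance of a single-time-point log-CK comparison rises about 16% to 47%, or 11% to 74% over the SD range, with less or no inflation for the D11 pre-to-post log change. The true size cannot be computed from the documents. The change is worth making before the first visit, because training that was not recorded at the time cannot be reliably recovered afterwards.

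**What to change.** 1. Reconcile sections 2 and 9 with section 10.3. Keep the usual routine during supplementation, but set one common exercise-free interval for every man before the D1 and D11 visits. The sponsor sets its length. Use it as the definition of muscle rest.
2. State one common activity rule from the end of the 24-hour rest to the day-2 pain score.
3. Add to the existing electronic diary the date and type of the last session before each visit, and of every session between D11 and day 7.
4. Report day-7 pain descriptively, alongside the training done since D11.

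No new measurement should be attached to the 24-hour blood draw until the schedules agree: section 10.3 includes it, but sections 2 and 8 do not.

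The cost is a revised participant instruction and an extra diary question. The downside is that men may skip one or two sessions around each visit, a small departure from their habitual routine.
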